² EOT visit should be conducted 21 \pm 2 days after the last infusion. Early withdrawal visit should be conducted within 21 days after the patient received the last dose of study treatment.

³ Follow-up visits will be performed after the patient completes EOT visit or early withdrawal visit. Follow-up visits will be scheduled every 3 weeks for 9 weeks, thereafter every 9 weeks until the end of the study. These visits can be conducted by phone.

⁴ Starting from cycle 4, there will be no study visit on Day 15.

⁵ All AEs including SAEs must be reported from the time of informed consent signed and must continue to be followed for 28 days after last administration of study treatment.

⁶ ECG will be performed prior to study drug administration, within 1 hour following study drug administration, 2 hours after study drug administration, immediately after the 3 hour infusion, 4 hours after study drug administration, and 24 hours after administration of the study drug. Starting from Cycle 4, the ECG will be obtained at every treatment cycle within 1 hour following study drug administration and at EOT/early withdrawal visit (time window: ± 5 min).

⁷ Tumor assessments should be performed at baseline, and every 3 cycles prior to next cycle until progression of disease. For patients who meet DC criteria after the first 3 cycles of study treatment, additional radiological tumor assessments should be performed at Week 12. Any additional assessment can be arranged when clinically indicated.

⁸ Test results within 7 days prior to Cycle 1, Day 1 (C1D1) are acceptable. Only items not performed or obtained within 7 days prior to C1D1 should be tested.

⁹ Serum pregnancy test for women of childbearing potential must be performed \leq 14 day prior to first dose.

¹⁰ Quality of Life questionnaires (EORTC QLQ-C30 and H&N35) should be performed at Screening and all clinic visits (before study drug administered, where applicable, except at C1D1).

¹¹ PK blood samples will be taken immediately pre-infusion then at 2, 3, 4, 6, 10, 21 and 24 hours after start of infusion on Day 1 and Day 8 of Cycles 1, 2 and 3 (time window: ± 5 min).

¹² Blood Sample for VEGF and CEC will be taken immediately pre-infusion then at 6, 10 and 24 hours after start of infusion on C1D1 and C3D15. Blood Samples for CEP will be taken immediately pre-infusion and C3D15.

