3.5. Follow-up

After discontinuation of study treatment, all patients will be followed for survival and disease-specific therapies of the clinician's choice will be administered. The data will be collected and can be done by telephone. Follow-up visits will be scheduled every 3 weeks for 9 weeks, thereafter every 9 until the end of the study.

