7.2. Adverse Event Reporting

All AEs occurring during the study (from the time of informed consent obtained until 28 days after the last dose of study treatment) observed by the Investigator or reported by the patient (whether or not attributed to study drug), will be reported on the eCRF. Clinically significant AEs considered related or non-related to the IP by the Investigator or the Sponsor will be followed until resolved or considered stable by the Investigator. The following information must be provided: description; dates of onset and resolution; severity; assessment of relatedness to IP, other suspect drug, or device; and action taken. The investigator may be asked to provide follow-up information.

All AEs, serious or not, that result in the patient's permanent withdrawal of IP or from the study will be discussed between the investigator and medical monitor. The eCRF for EOT/Early Withdrawal Visit should be completed including reason of withdrawal.

It will be the investigator's clinical judgment whether or not an AE is of sufficient severity to require the patient's removal from study treatment. A patient may also voluntarily withdraw from study treatment due to what he or she perceives as an intolerable AE. If either of these occurs, the patient must undergo EOT assessment and be given appropriate care under medical supervision until symptoms cease or the condition becomes stable.

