7.4. Serious Adverse Event Reporting

All SAEs, irrespective of relationship to IP, must be reported within 24 hours of the Investigator knowledge of the event to the Sponsor or CRO. In particular, if the SAE is fatal or life-threatening, notification to the Sponsor must be made immediately, irrespective of the extent of available AE information. This timeframe also applies to follow-up information on previously forwarded SAE reports as well as to the initial and follow-up reporting of exposure during pregnancy and exposure via breast feeding cases.

Relevant medical records should be provided to the Sponsor or CRO as soon as they become available; autopsy reports should be provided for deaths if available. Should an Investigator be made aware of an SAE occurring any time after the reporting period, it must be promptly reported.

All SAEs that have not resolved by the end of the study, or that have not resolved upon discontinuation of the patient's participation in the study, must be followed until any of the following occurs:

- The event resolves.
- The event stabilizes.
- The event returns to baseline, if a baseline value/status is available.
- The event can be attributed to agents other than the IP or to factors unrelated to study conduct.
- It becomes unlikely that any additional information can be obtained (patient or health care practitioner refusal to provide additional information, lost to follow-up after demonstration of due diligence with follow-up efforts).

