8.4. Safety Analysis

Safety profile will be evaluated by the following endpoints.

- Hematology, clinical chemistry, coagulation factors and urinalysis laboratory data changes
- AE incidence/SAE incidence
- Physical examination result changes
- Vital sign changes
- Electrocardiogram (ECG) (including PR, QRS, QT, QTc, and RR intervals) results

All safety endpoint data will be listed and summarized for each dose and day within cycle using descriptive statistics. The change from baseline data for the safety endpoints will also be summarized using descriptive statistics.

Number and percentage of patients experiencing at least one DLT or AE will be tabulated by dose. Further details regarding any DLTs or AEs experienced will be provided in data listings. All recorded AEs will be listed and tabulated by system organ class and preferred term using the Medical Dictionary for Regulatory Activities (MedDRA) and by dose level. The incidence of Treatment Emergent AEs (TEAEs) during the study period will be tabulated by dose group, body system, and preferred term. TEAEs are those events that occur or worsen on or after first dose of IP and up to 28 days after the last dose. TEAEs are AEs with onset dates on or after the first dosing date. Those with missing onset dates will be included as treatment emergent. Number and percentage of patients who withdrew/stopped dosing will be tabulated. Number and percentage of patients who missed 1 or more doses (1 dose, 2 doses, etc.) in any cycle will be tabulated by cycle.

Serious AEs, Grade 3 and above AEs, AEs related to study treatment, and AEs causing discontinuation will be tabulated. AEs for individual patients will be listed, along with information regarding onset, duration, severity, and relationship to study treatment.

Vital signs, physical examination, ECG, and clinical laboratory test results will be listed and summarized by dose group, cycle and day within cycle as applicable and may be presented graphically. Any significant or outside normal range limits value for vital signs, physical examination, ECG, or clinical laboratory results will be listed

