9.1. Adverse Events

Adverse events (AEs) will be coded using the Medical Dictionary for Regulatory Activities (MedDRA®, Version 19.1 or higher), and data will be summarized by System Organ Class (SOC) and Preferred Term (PT). The number and percent of subjects reporting each AE will be summarized for each dose level (cohort) and overall. A subject with two or more AEs within the same level of summarization (i.e., SOC or PT) will be counted only once in that level using the most severe (i.e., highest severity/grade) event or most related (for the relationship to study drug table). Percentages will be based on the number of subjects in the Safety Population within each dose level (cohort). The number of AEs reported will also be presented.

Treatment-emergent AEs (TEAEs) are defined as pre-treatment existing conditions that worsen after study drug administration, or events that occur during the course of the study during or after administration of study drug. Only TEAEs will be included in the AE summary tables which will present data by dose level (cohort). The cohorts to be included in each table are listed in section 3. In the case of a missing AE start date or stop date, the most conservative approach will be followed to classify AE into TEAE.

An overall summary of AEs will be produced including the number of TEAEs; the number and % of subjects reporting at least one: TEAE, serious TEAE, Dose Limiting Toxicity (DLT), grade 3 or higher TEAE, TEAE related to study treatment (possibly, probably, or definitely related), serious TEAE related to study treatment, grade 3 or higher TEAE related to the study drug, TEAEs by maximum severity and TEAEs by maximum relationship.

Additional AE tables will be generated as follows:

- TEAEs by SOC and PT
- Study Medication Related TEAEs by SOC and PT
- TEAEs by (Maximum) Severity
- TEAEs by (Maximum) Relationship to Study Medication
- Grade 3 or Higher TEAE by SOC and PT
- Treatment Emergent SAEs
- Study Medication Related SAEs by SOC and PT
- Dose Limiting Toxicity (DLT) by SOC and PT
- TEAEs Leading to Study Medication Permanently Discontinued
- TEAEs Leading to Study Medication Interrupted
- TEAEs Leading to Death
- Duration from Last Dosing to the Start of TEAE (days of each TEAE since its immediate last dosing)

A by-subject AE data listing, including verbatim term, MedDRA SOC and PT, severity, outcome and relationship to study treatment, will be provided. A separate listing will be generated for SAEs.

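### SAP 9.1 leaves the treatment-emergent window open-ended and does not resolve or flag the conflict between two definitions in protocol 8.4, so late-reported SAEs could enter the TEAE tables.

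*SAP*

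**What the plan says.** **The protocol's two definitions.** Protocol 8.4 (Safety Analysis) first says "TEAEs are those events that occur or worsen on or after first dose of IP and up to 28 days after the last dose". The next sentence says "TEAEs are AEs with onset dates on or after the first dosing date", with no upper limit.

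**The SAP's definition.** SAP 9.1 (Adverse Events) counts pre-existing conditions that worsen after dosing and "events that occur during the course of the study during or after administration of study drug". It gives no end to the window. The same section restricts the AE summary tables to treatment-emergent events.

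**What is collected.** Protocol 7.2 has AEs recorded on the eCRF "from the time of informed consent obtained until 28 days after the last dose of study treatment". Footnote 5 to both study schedules (protocol Tables 1 and 2) agrees: AEs "must continue to be followed for 28 days after last administration of study treatment". Protocol 7.4 adds one route for later events: "Should an Investigator be made aware of an SAE occurring any time after the reporting period, it must be promptly reported".

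**What happens after treatment stops.** Protocol 3.5 says "After discontinuation of study treatment, all patients will be followed for survival". The follow-up contacts also record later systemic therapy, radiotherapy and surgery, which SAP 9.2 lists separately. Neither document ends the treatment-emergent window when new cancer therapy starts.

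**Flagging of changes.** Protocol 8.1 undertakes to highlight significant analysis changes in the SAP. SAP section 4 does this for the analysis populations. SAP 9.1 says nothing comparable about the TEAE window.

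**The concern.** A treatment-emergent table is interpretable when its window matches the period in which events are looked for in the same way in every subject. Here that period closes 28 days after the last dose. Under the SAP wording the table window stays open until the end of the study.

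Take a subject who stops early, starts other chemotherapy and has a serious infection three months after the last SCB01A dose. The SAP wording makes this a treatment-emergent SAE at that subject's SCB01A dose. Protocol 8.4 excludes it under its first sentence and includes it under its second. The analyst therefore has no settled rule, and the report's reader cannot tell which one was used.

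The SAP introduction says that, with so few subjects, the analysis will focus on safety. The treatment-emergent tables are thus a main output of the report, and each subject carries a large share of every percentage.

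**Working it through.** The plan gives no figure that depends on this window, so there is nothing to reproduce. The check compares the texts and then does calendar and denominator arithmetic.

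**1. Windows side by side**

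| Source | Start | End |
|---|---|---|
| Protocol 8.4, first sentence | first dose | last dose + 28 days |
| Protocol 8.4, second sentence | first dosing date | none |
| SAP 9.1 | administration of study drug | none (course of the study) |
| Protocol 7.2 (eCRF recording) | informed consent | last dose + 28 days |
| Protocol 7.4 (late SAEs) | after the reporting period | none; only if the investigator becomes aware |

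Only the first sentence of 8.4 ends where systematic recording ends.

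**2. What can fall in the gap.** Ordinary AEs are not due to be recorded beyond day 28 after the last dose. The clear remaining route is protocol 7.4: SAEs, including fatal ones, that the investigator happens to learn of. Section 7.4 concerns notification to the sponsor or CRO and does not say that such SAEs go onto the eCRF. SAP section 3 works from eCRF data, so entry into the tables is conditional.

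**3. When follow-up contacts fall.** The end-of-treatment visit is 21 ± 2 days after the last infusion (protocol 3.4), and the first follow-up is taken as 3 weeks later:
- earliest: 19 + 21 = 40 days after the last dose
- latest: 23 + 21 = 44 days after the last dose

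For a subject with an end-of-treatment visit on that schedule, every follow-up contact is therefore beyond day 28.

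**4. Length of the gap under the planned schedule.** The planned end of study is 36 weeks after the last patient's first dose: 36 × 7 = 252 days, taken as Day 252 for that patient and later for earlier patients.
- Last dose at Cycle 3 Day 8 (Day 50): the 28-day window ends on Day 50 + 28 = 78. The open window adds at least 252 − 78 = 174 days, and 174/252 = 69%.
- Single dose on Day 1: the window ends on Day 1 + 28 = 29. The open window adds at least 252 − 29 = 223 days, and 223/252 = 88%.

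These are days of definition, not days of routine AE collection. The trial was terminated early and the actual follow-up is not stated, so they describe the plan and not what occurred.

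**5. Effect of one late SAE in a subject with no earlier SAE**
- Overall: 1/5 = 20.0 percentage points.
- By cohort: the SAP does not give the split. If 3 subjects were at Dose 1 and 2 at Dose 2 (an assumption), 1/3 = 33.3 and 1/2 = 50.0 points. Across cohort sizes of 4 down to 1, the range is 1/4 = 25 to 1/1 = 100 points.

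**The case against.** **The SAP does not simply drop a protocol rule.** A reader might infer that it discards a clear 28-day limit. The documents do not support that: the second sentence of protocol 8.4 is itself open-ended, and the SAP agrees with it. The defect is an unresolved contradiction that the SAP carries forward without comment. This stands.

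**Months of follow-up events will not pour in.** A reader might also infer that all AEs during survival follow-up count as treatment-emergent. Protocol 7.2 stops routine recording at 28 days, so the exposure is mainly late SAEs and deaths. The schedule tables as extracted mark AE review under follow-up phone calls. That column also shows imaging and urinalysis, while the end-of-treatment column lacks assessments that protocol 3.4 requires. The columns are probably misaligned, and nothing here rests on them.

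**Late events would be visible.** The AE, SAE, dosing, discontinuation and later-therapy listings will all be produced, as will Table 14.3.2.13 (time from last dosing to TEAE start). The analysis is descriptive, with no formal comparison of doses. This limits the harm, but visibility in a listing does not remove an event from the incidence tables.

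**A wider window is more cautious.** That would be fair if the extra time were observed evenly. It is not: its length depends on when a subject stops, and its content depends on what the investigator happens to hear.

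**A hard cut-off could hide late drug-related events.** This stands, and it is why the fix needs a separate listing that shows relationship to study drug.

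**Conclusion.** The point holds in limited form. Protocol 8.4 contradicts itself on when the treatment-emergent window closes, and SAP 9.1 uses the open-ended version without flagging a departure from the 28-day limit. The textual finding is certain. The numerical effect is conditional: it needs an SAE later than 28 days after the last dose, in a subject with no earlier SAE, that enters the analysis database. Neither document reports one. If it happened, overall treatment-emergent SAE incidence would move by 20 points among five subjects. Cohort figures would move more, by an amount that depends on a split the SAP does not state.

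Restoring the 28-day limit would not separate SCB01A from all later therapy. Events under new treatment started within 28 days of the last dose would still count. The change is worth making because it is small, it aligns the tables with the period of systematic collection, and safety is the report's main content.

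**What to change.** - **SAP 9.1:** define TEAEs as events that start or worsen from the first dose to 28 days after the last dose. Keep the existing conservative rule for missing dates. State that this resolves the two definitions in protocol 8.4.
- **Protocol 8.4:** reconcile the two sentences. With enrolment over, a clarification in the SAP and the study report can serve if no further amendment is planned.
- **Tables:** apply the window to the TEAE tables marked for production: 14.3.2.1, 14.3.2.2, 14.3.2.3, 14.3.2.7 and 14.3.2.13. Leave Table 14.3.2.9, and the DLT row of 14.3.2.1, on the DLT criteria in protocol 6.2.
- **Later events:** list them separately as post-treatment, with days since last dose, relationship to study drug and any later cancer therapy, so that late drug-related events stay visible.

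The cost is one sentence in the SAP, one date condition in the AE derivation and one short listing. The plan already collects dosing dates, AE onset dates and later therapy, so no new data are needed.

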9.2. Concomitant medication

Concomitant medications will be coded using World Health Organization Drug Dictionary (WHO-DD, September 2016 or higher). Concomitant medications are medications taken at least once after the start of first study-drug administration. Medications stopped prior to the day of the start of first study-drug administration will not be considered concomitant medication. The prior medication will not be summarized, but they will be listed along with concomitant medications. Only concomitant medications will be summarized.

Individual data listings will be presented for each subject and summarized by WHO-DD Anatomical Therapeutic Chemical (ATC) anatomical group, and preferred term using frequency counts and percentages. Subjects who take the same medication more than once will be counted only once for that preferred term.

Follow-up visits were scheduled after end of treatment or early withdrawal visit with regards to cancer radiation therapy, cancer systemic therapy, or cancer surgery. These treatments, if any, will be listed separately.

9.3. Laboratory

9.3.1. Laboratory Parameters

Hematology Parameters

- WBC
- Neutrophils
- Lymphocytes
- Monocytes
- Eosinophils
- Basophils
- Red blood cell (RBC)
- Hematocrit (Hct)
- Hemoglobin
- Mean corpuscular volume (MCV)
- Mean corpuscular hemoglobin (MCH)
- Mean corpuscular haemoglobin concentration (MCHC),
- Platelet count

Chemistry Parameters

- Blood urea nitrogen (BUN)
- Creatinine
- AST
- ALT
- ALP
- Total Bilirubin
- Albumin
- Calcium
- Glucose
- Uric Acid
- Potassium
- Total creatine kinase (Ck) (if total Ck is above the ULN for the laboratory, Troponin-T or Troponin-I will be determined)
- Gamma-glutamyl transferase (GGT)
- Total cholesterol
- High-density lipoprotein (HDL)
- Low-density lipoprotein (LDL)
- Triglycerides (TG)
- Amylase
- Lipase

Coagulation Parameters

- Prothrombin Time
- INR

Urinalysis Parameters

- Specific gravity
- pH
- Protein
- Glucose
- Leucocytes
- Erythrocyte
- Nitrite
- Ketone body
- Urobilinogen
- Bilirubin
- RBC
- WBC
- Hyaline
- Cast
- CAOX
- Crystal
- AMOR
- Mucus

9.3.2. Biostatistical methods

All hematology, chemistry and coagulation parameters will be summarized using descriptive statistics for each dose level (cohort) for all time points assessed, including change from baseline (last pre-dose value) for all post-dose assessments. All continuous parameters will be summarized using the units reported from the laboratory.

Urinalysis will be summarised as categorical data by using frequency and percentage, as appropriate, except for specific gravity and pH which will be treated as continuous data.

Subjects with abnormal laboratory values will be summarized for each laboratory parameter by study visit and by dose cohort. The frequency counts and percentages of subjects with laboratory value out of reference range (low/high) and their clinical significance (if any data) will be summarized. Shift tables from Cycle 1, Day 1 (pre-dose) to all follow-up visits will also be generated for each chemistry laboratory parameter with values of Within Normal Limits (WNL), High, and Low used for the shift categories.

All laboratory data will be included in the by-subject data listings. Laboratory values will be compared to normal range of the single local laboratory and values that fall outside of the normal ranges will be flagged as: H (High) and L (Low) in the data listings.

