T _{max}	Time to Maximum Concentration
ULN	Upper Limit of Normal
V _d	Volume of Distribution
VEGF	Vascular Endothelial Growth Factor

Abbreviation	Definition
WBC	White Blood Cell

SYNOPSIS

Title of Study:	An Open-Label, Phase II Study to Evaluate SCB01A in Patients with Recurrent or Metastatic Squamous Cell Head and Neck Cancer who have Received Platinum-Based Treatment
Sponsor:	SynCore Biotechnology Co., Ltd. [name]
Principal/Coordinating Investigator:	[name], Director, Keelung Chang Gung Cancer Center, Keelung Chang Gung Memorial Hospital, Keelung, Taiwan
Investigational Product (IP):	SCB01A
Protocol Number:	SCB01A-21
Indication:	Recurrent or metastatic squamous cell carcinoma of head and neck
Phase of Development:	Phase II
Study Centers:	4–8 sites in Taiwan

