5.5. Safety Laboratory Assessments

The local laboratory for the study site will be used and all procedures will be performed following the standard operating procedure (SOP) of the local laboratory.

Hematology and clinical chemistry blood samples will be obtained at screening, all clinic visits and the EOT/Early Withdrawal visit. Coagulation will be determined at all clinic visits (excluding screening). During the run-in phase minimum of 19 samples (180 ml) will be taken. The number of sample might differ based on actual number of cycles completed and if there are any unscheduled visits done.

Urinalysis will be determined at Screening and Day 1 of each cycle prior to study treatment administration.

The parameters assessed are detailed below:

Hematology

WBC with differential, red blood cell (RBC), hematocrit (Hct), Hb, mean corpuscular volume (MCV), mean corpuscular hemoglobin (MCH), mean corpuscular hemoglobin concentration (MCHC), platelet count

Clinical Chemistry

Blood urea nitrogen (BUN), Creatinine, AST, ALT, ALP, Total Bilirubin, Albumin, Calcium, Glucose, Uric Acid, Potassium, Total creatine kinase (Ck) (if total Ck is above the ULN for the laboratory, Troponin-T or Troponin-I will be determined), gamma-glutamyl transferase (GGT). Total cholesterol, high-density lipoprotein

(HDL), low-density lipoprotein (LDL), triglycerides (TG), amylase and lipase will be tested at the Screening Visit.

Coagulation

PT, INR

Urinalysis

Specific gravity, pH, protein, glucose, leucocytes, erythrocyte, nitrite, ketone, urobilinogen, bilirubin and sediment including RBC, WBC, Hyaline, Cast, CAOX, Crystal, AMOR and mucus.

Pregnancy test

A serum beta-HCG test for women of childbearing potential will be performed \leq 14 days prior to the first dose of study treatment.

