6.3. Safety Measurements

The following safety assessments will be done during the study:

- Incidence and intensity of AEs evaluated using the CTCAE version 4.03
- Incidence and intensity of clinically significant abnormal laboratory values evaluated using the CTCAE version 4.03
- Percentage of patients experiencing dose adjustments, including delays or discontinuation of study medication
- Physical examination findings
- Vital signs measurements
- ECG (including PR, QRS, QT, QTc and RR intervals) findings

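### SAP 9.3.2 derives no CTCAE grade for laboratory values, although protocol 6.3 names their CTCAE intensity as a safety measurement, and the SAP does not highlight the omission

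*SAP*

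**What the plan says.** **Protocol.** Section 6.3, like the synopsis, lists this safety measurement: "Incidence and intensity of clinically significant abnormal laboratory values evaluated using the CTCAE version 4.03". Section 5.5 names no central laboratory: "The local laboratory for the study site will be used". The synopsis plans "4–8 sites in Taiwan". Section 8.1 requires significant departures from the protocol's analyses to be highlighted in the SAP.

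**SAP 9.3.2.** Hematology, chemistry and coagulation get descriptive statistics and change from baseline by dose level. On units: "All continuous parameters will be summarized using the units reported from the laboratory". On abnormal values, the frequency of subjects with "laboratory value out of reference range (low/high) and their clinical significance (if any data) will be summarized". On reference ranges: "Laboratory values will be compared to normal range of the single local laboratory and values that fall outside of the normal ranges will be flagged" (H or L, in the listings). On shifts: "Shift tables from Cycle 1, Day 1 (pre-dose) to all follow-up visits will also be generated for each chemistry laboratory parameter", in the categories normal, high and low. The section does not mention CTCAE.

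**SAP 18 and 19.** Only items marked Y will be produced. The out-of-range tables (14.3.4.5 to 14.3.4.7) and the laboratory listings (16.2.8.1 to 16.2.8.4) are marked. The laboratory shift tables (14.3.4.8 to 14.3.4.10) are not, although 9.3.2 says that the chemistry shifts will be generated.

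**The concern.** After early termination with five patients, SAP section 1 makes safety the focus of the report. A safety measurement that the protocol names should then either be delivered or be openly dropped. Here it is neither.

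A high/low flag carries direction but no intensity. In this trial intensity matters: five of the nine DLT criteria in protocol 6.2 rest on graded neutrophil, platelet or hemoglobin findings. Without a grade derived from the measured value, the laboratory outputs give no systematic check, independent of the investigator's adverse event reporting, on how severe the abnormalities were.

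A smaller point concerns the reference range. One laboratory's normal range does not fit a plan in which each site uses its own laboratory, and the SAP gives no rule for several ranges or units.

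**Working it through.** No sample size, power or event figure is involved. The check sets the sections side by side.

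1. **Promised against delivered.** Protocol 6.3 asks for incidence and intensity by CTCAE v4.03, for clinically significant abnormal values. SAP 9.3.2 delivers incidence of low or high, and clinical significance if collected. Intensity is missing for every parameter in the laboratory outputs.

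2. **Is the change highlighted?** SAP section 4 says openly that the analysis populations were modified. Neither section 9.3.2 nor section 15 says that laboratory grading was left out.

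3. **Can the flags show worsening?** Protocol 3.8.1 admits ALT, AST and ALP below 3 × ULN, and bilirubin and INR up to 1.5 × ULN. Let a patient enter at *a* × ULN with *a* > 1, and let the value later rise by a factor *k* > 1. Then *k* × *a* > *a* > 1, so the flag is High both times. With illustrative values *a* = 2 and *k* = 3, ALT goes from 2 × ULN to 3 × 2 = 6 × ULN and is still High to High. The same holds for a falling count that starts below the lower limit of normal. Entry is allowed with platelets just above 75 × 10⁹/L and hemoglobin just above 9 g/dL. Whether such values lie below the limit depends on laboratory ranges that the documents do not give.

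4. **Does severity reach the report by another route?** In part. Protocol 7.1 lets an abnormal laboratory finding be an adverse event, and 7.1.1 grades adverse events by CTCAE. These outputs are marked Y:
   - overall summary 14.3.2.1, which under SAP 9.1 includes grade 3 or higher events and maximum severity;
   - DLT table 14.3.2.9;
   - adverse event listing 16.2.7.1, with severity.

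   These are not marked Y:
   - table 14.3.2.4 (maximum severity);
   - table 14.3.2.6 (grade 3 or higher by term);
   - listing 16.2.7.3 (DLTs).

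5. **How far can the single range reach?** Five patients can come from 1 to 5 laboratories; the documents do not say how many. If one laboratory's range is applied to all and that laboratory served *m* patients (*m* = 1 to 5), then 5 − *m* patients are judged against another laboratory's range. That is 5 − 5 = 0 at best and 5 − 1 = 4 at worst.

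**The case against.** The other side has four good arguments.

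- **The SAP reports more than flags.** It gives descriptive statistics, change from baseline and every laboratory value by patient. With five patients a reader can find an extreme value and grade it by hand. This stands. A reader might infer that severe toxicity is indistinguishable from a trivial deviation anywhere in the report. The documents do not support that: the loss is confined to the flags, the out-of-range tables and the shift categories.
- **Clinically significant findings should appear as graded adverse events.** This stands in part. The route works only if the investigator reports the finding, and three of the outputs that would show severity or DLTs in detail will not be produced.
- **Protocol 8.4, the safety analysis section, names no CTCAE laboratory table, and 6.3 covers only clinically significant values.** Both are true, and they limit what was promised. They do not remove the measurement named in 6.3. Nor would a grade alone settle every DLT: of the five laboratory-based criteria, three also need duration or complications.
- **The SAP was written after termination, so its reference to one laboratory may simply be a fact.** This may be right. A reader might infer from the planned number of sites that most values would meet the wrong range, or that means will mix units. The trial stopped at five patients, and no passage shows a second laboratory or a unit difference.

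**Conclusion.** The concern holds in limited form. SAP 9.3.2 does not deliver the intensity part of a safety measurement that the protocol names, and it does not say so. Within its abnormality flags and out-of-range tables, all grades in one direction collapse into a single category, and worsening from an abnormal baseline is hidden. This conclusion rests only on the two documents' text and does not depend on the number of laboratories.

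The reference-range point is conditional. It affects nobody if one laboratory contributed, and at most 4 of the 5 patients otherwise; the count of 1 to 5 laboratories is an assumption.

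The practical weight is modest, because the report is descriptive and the raw values are listed. It is still more than missing detail: the correction is cheap and concerns the part of the report that the SAP calls its focus.

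**What to change.** In SAP 9.3.2:

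- Derive the CTCAE v4.03 grade for each gradable parameter from the collected values, and add a grade column to listings 16.2.8.1 to 16.2.8.3.
- Report the worst post-baseline grade, with the baseline grade, by dose level. With five patients this is one short table.
- Flag each value against the normal range of the laboratory that analysed it, and convert to common units before summarising.
- State how many laboratories contributed. If it was one, that sentence settles the range and unit question.
- Make the shift-table statement in 9.3.2 agree with section 18.

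If the sponsor prefers not to grade laboratory values, the SAP and the study report should say that this measurement from protocol 6.3 was dropped, and why.

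The cost is SAP wording and modest programming on data already collected. No new data or patients are needed.
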